#### 4.2 Analysis sets and subgroups

Data will be analysed to determine the outcomes and possible risk factors for CDI based on the different diagnostic criteria. Comparisons will be made between outcomes and risks for different countries and healthcare settings (hospital, community). Sample size will be too small to perform subgroup analysis within each country.

#### 5. Handling of missing values and other data conventions

Where data is unknown, 'data unavailable' will be entered onto the data management system. Patterns of missing data will be described. Where an individual has a missing value for one of the study outcomes, they will be excluded from the analysis of that outcome. Sensitivity analysis can be used to determine the potential effect of missing data.

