#### 3.2.2 Outcome measures

Primary outcome measure: Crude mortality at 30 days and 6 months after the sample was taken will be compared between case and controls, those that received a correct diagnosis at the original hospital and those that were 'missed' (either due to lack of testing or inadequate testing) and between community and hospitalised patients.

Secondary outcome measures: Patient length of stay, severity of infection (e.g. WCC, serum albumin, temperature), need for escalation of medical/surgical care due to gastrointestinal disease, post-infectious sequelae.

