#### 3.2.6 Data collection

Data will be collected via a standardised CRF, with a full supporting SOP. The CRF will be completed by the clinical care team at the participating site that submitted the sample (during O1.1). The CRF will not contain any participant identifiable data; all data will be held against a pseudoanonymised study code, with the link back held by the clinical care team only. COMBACTE-CDI investigators will not access participant's notes or access the link back. Once the CRF data has been collected and validated and verified the link-back will be destroyed by the local study site.

Data will be collected on the following variables on outcomes of CDI;

- Evidence of other enteric pathogens (+/- 7 days of the original sample)?
- Symptoms at time of the sample
- Alternative cause for the patient's diarrhoea documented (e.g. laxatives, pathogen)?
- Duration of diarrhoea/non-normal bowel habit?
- Primary/recurrent CDI
- Antibiotics at the time of the sample or the preceding 3 months?
- Evidence of colitis?
- Evidence of post-infectious diarrhoea

- CDI Severity markers (Temperature (nearest reading +/- 3 days of the sample), serum creatinine (nearest reading +/- 3 days of the sample), White cell count (nearest test +/- 3 days of the sample)
- Treatment for CDI episode
- Was treatment for CDI/diarrhoea escalated medical/surgical?
- Outcome 30 days and 6 months after the sample (discharged, in-patient, died)
- Length of stay

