#### 2. Data source

Retrospective case note data is collected on paper case report forms (CRFs) before upload onto an electronic data management system by the European coordinator.

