## 7. Statistical methodology and statistical analysis

#### 7.1 Descriptive analysis

Distribution of demographic, concomitant pathogens, medical conditions, medical procedures, and medication used will be tabulated by case and controls. The analysis will also be stratified by age group (<18, 18-49 years, 50+ 50-64 years, 65 +, 65--84 years, and 85 + years).

Where data are continuous variables, means and standard deviations will be presented; where these data have a highly skewed distribution, medians, 25th and 75th percentiles will be presented. Where data are categorical variables, the number and percentage of participants within each category will be presented. The percentage of missing values will be reported for each variable (continuous or categorical).

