10.3	If the sample was	Binary	Univariate/multivariate	Up to six months		
	taken as a hospital	-		after the index		
	inpatient, was the			sample		
	patient discharged	Continuous	Univariate/multivariate			
	>30 days after the	(no. of				
	sample	days)				
If the sam	ple was taken as a con	nmunity				
patient	•	-				
10.4	Was the patient	Binary	Univariate/multivariate	Up to 30 days		
	admitted to			after the index		
	hospital			sample		
10.4.1	If yes, please give	Continuous	Univariate/multivariate	Up to 30 days		
	dates of the	(no. of		after the index		
	subsequent	days)		sample		
	hospital admissions					
If the sam	If the sample was taken as a hospital inpatient or a community patient					
10.5	Did the patient die	Binary	Univariate/multivariate	Up to 30 days		
	in the 30 days after			after the index		
	the sample			sample		
		Continuous	Univariate/multivariate			
		(no. of				
		days)				
10.5.1	If yes, was the	Binary	Univariate/multivariate	Up to 30 days		
	death linked to CDI			after the index		
				sample		
10.6	Was the patient	Binary	Univariate/multivariate	Up to six months		
	admitted to			after the index		
	hospital between			sample		
	30 days and 6					
	months after the					
	sample					
10.6.1	If yes, please give	Continuous	Univariate/multivariate	Up to six months		
	the dates of	(no. of		after the index		
	hospital admissions	days)		sample		
10.7	Did the patient die	Binary	Univariate/multivariate	Up to six months		
	between 30 days			after the index		
	and 6 months after			sample		
	sample?	Continuous	Univariate/multivariate			
		(no. of				
		days)				
10.7.1	If yes, was the	Binary	Univariate/multivariate	Up to six months		
	death linked to CDI			after the index		

		sample

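### Excluding patients with a missing outcome can bias the primary mortality comparison where length of record contact differs between groups; the SAP commits to no analysis that would show it

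*SAP*

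**What the plan says.** **Outcome.** Protocol 3.2.2 sets the primary outcome of the outcomes study: "Crude mortality at 30 days and 6 months after the sample was taken will be compared between case and controls". The same measure is compared between correctly diagnosed and missed patients, and between community and hospital patients.

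**Source.** SAP section 2 describes retrospective case notes transcribed to paper forms. Protocol 3.2.6 has the form completed by the clinical team at the submitting site. Protocol 2.4.2 requires sites to be able to obtain outcome data themselves or through the place that sent the sample. Neither document names a death register, an active vital-status check, or a rule for a patient whose notes simply stop.

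**Missing data.** SAP section 5 says "Where data is unknown, 'data unavailable' will be entered onto the data management system", then "Where an individual has a missing value for one of the study outcomes, they will be excluded from the analysis of that outcome". It promises a description of missing-data patterns and adds: "Sensitivity analysis can be used to determine the potential effect of missing data". SAP 7.1 commits to the percentage missing for every variable.

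**Recording of death.** Protocol 3.2.6 lists "Outcome 30 days and 6 months after the sample (discharged, in-patient, died"). SAP Appendix 1 has yes/no items beginning "Did the patient die", one for the first 30 days (10.5) and one for 30 days to 6 months (10.7), each with a number of days.

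**Analysis.** SAP 7.2 compares categorical variables by chi-squared or Fisher's exact test. No method for censored follow-up is given.

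**The concern.** Whether a patient has a known 6-month status depends partly on what that status is. A recorded death settles the item at once. A survivor settles it only if something in the notes shows the patient alive at 6 months. Of two patients whose contact ends on day 100, one who died on day 60 is analysed and one who was alive at day 100 is removed. Partial follow-up that shows survival is lost, while partial follow-up that shows death is kept.

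If this happened equally everywhere, each group's mortality would be overstated and the comparison would suffer less. The groups compared may well differ in contact. Protocol 3.2.1 itself expects a patient discharged to the community to be seen later through a different laboratory. Central results are not returned to sites (Protocol 5.0), so a missed case need not get the follow-up of a recognised one. A primary mortality comparison could then partly measure how long patients stay visible in the notes. The opposite error is also possible: deaths elsewhere, after contact ends, may not reach the site.

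**Working it through.** The documents state no mortality rate, no expected missing fraction and no power calculation for mortality, so there is no figure to reproduce. The calculations below are illustrations. Every rate in them is assumed except the group sizes, which come from SAP Table 1 (213 cases, 512 controls).

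**1. Contact ends independently of death.** Assumptions: true 6-month mortality m = 0.20 in both groups; deaths spread evenly over 180 days; a fraction c has contact to 6 months; in the rest, last contact falls evenly over the 180 days, so half of their deaths are seen.

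- Fraction of deaths known: kd = c + (1 − c) × 0.5
- Fraction of survivors known: ks = c
- Mortality after exclusion = m·kd / [m·kd + (1 − m)·ks]

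| c | kd | ks | Mortality after exclusion |
|---|---|---|---|
| 0.80 | 0.90 | 0.80 | 0.18 / (0.18 + 0.64) = 22.0% |
| 0.60 | 0.80 | 0.60 | 0.16 / (0.16 + 0.48) = 25.0% |

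The apparent risk ratio is 22.0/25.0 = 0.88 where the truth is 1.00. A simulation of the same set-up gives Kaplan-Meier estimates of about 20% in both groups, so censoring removes the bias in this case.

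**2. Deaths missed more often in one group.** With exclusion, the observed odds ratio equals the true one multiplied by (deaths known / survivors known in cases) ÷ (deaths known / survivors known in controls). Suppose 95% of survivors are known in both groups and 95% of case deaths are known. If 80% of control deaths are known, the factor is (0.95/0.95) ÷ (0.80/0.95) = 1.19. If 70% are known, it is (0.95/0.95) ÷ (0.70/0.95) = 1.36. The bias now runs the other way.

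**3. Missingness unrelated to death within each group.** If 5% of cases and 20% of controls are missing whatever their vital status, the factor is (0.95/0.95) ÷ (0.80/0.80) = 1.00. Unequal missingness alone does no harm; it must also depend on death. Under the mechanism in step 1 it does, because a death within contact completes the item.

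**4. What mandatory bounds would show.** Assume about 10% observed mortality in both groups.

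- 5% of cases and 10% of controls unknown: 20 deaths in 202 cases, 46 in 461 controls. Lower bound 20/213 − (46 + 51)/512 = −9.6 points; upper bound (20 + 11)/213 − 46/512 = +5.6 points.
- 10% and 20% unknown: 19 deaths in 192 cases, 41 in 410 controls. Lower bound 19/213 − (41 + 102)/512 = −19.0 points; upper bound (19 + 21)/213 − 41/512 = +10.8 points.

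Even moderate unknown fractions leave the direction of a case-control difference open.

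**The case against.** **The plan does more than exclude.** It commits to describing missing-data patterns and reporting the percentage missing per variable, and Protocol 2.4.2 lets sites get outcomes from the sample source, which can be a community doctor or nursing home. This stands and may keep unknowns few. It does not change the exclusion rule, and a percentage per variable need not be split by case status or setting.

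**Contact may be similar in cases and controls.** SAP section 4 draws controls from the same site and setting. By Table 1, 156/213 = 73.2% of cases and 365/512 = 71.3% of controls are hospital patients, so setting largely balances. This weakens the case-control concern. It does not help the hospital v community or diagnosed v missed comparisons.

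**Censoring is not a cure.** This is the strongest point. Suppose 95% of deaths are known, with 80% v 60% of survivors known, and all unknown patients are last seen on day 5. Kaplan-Meier then gives 22.8% v 28.1%, a ratio of 0.81, the same as exclusion. With last contact spread evenly the ratio is 0.89. Some community patients will also have no later date to censor at. The bounds must therefore accompany the survival estimate.

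**A stronger reading that a reader might infer** from the three states in Protocol 3.2.6 is that patients lost from the notes are recorded as discharged and so counted as alive. The documents do not say this. SAP section 5 enters unknown data as unavailable, and Appendix 1 asks about death separately from discharge. What stands is narrower: being discharged does not establish vital status at 6 months, the protocol list has no unknown state, and neither document says how a site should answer for a patient discharged early with no later notes.

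**Conclusion.** The concern holds as a fault in the analysis rule for the primary mortality outcome. Exclusion is explicit, it covers 30-day and 6-month mortality, and the only analysis that could expose its effect is optional and unspecified. Exclusion tends to overstate mortality when contact simply runs out. It distorts comparisons when contact differs between groups, by about 22% v 25% under the assumptions in step 1. If deaths after contact are missed unequally, the bias can reverse. It is absent if missingness is unrelated to death within each group. The documents do not show which situation applies, and the size cannot be determined from them. They also do not establish that contact differs between cases and controls; that remains a plausible risk the plan should be able to detect.

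**What to change.** - **Replace exclusion for mortality** with time to death from the sample date, reporting Kaplan-Meier risks at 30 days and 6 months. Use the days-to-death items (10.5, 10.7). Censor at the last date known alive from any form date: discharge (10.1, 10.3), admissions (10.2.1, 10.4.1, 10.6.1), later CDI tests (4.3.1), and information from the sample source site.
- **Make best-case and worst-case bounds mandatory** for patients with unknown vital status, in place of the optional sensitivity analysis.
- **Report the unknown share** at 30 days and 6 months by case status and by setting.
- **Reconcile Protocol 3.2.6 with SAP items 10.5 and 10.7**: state that discharge alone is not vital status, add an unknown state, and tell sites how to answer when notes stop.

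The cost is SAP wording, one derived date and a short instruction to sites, with no new patients or visits. It needs settling before sites destroy the patient link after data querying (Protocol 1.4.2), because vital status cannot be recovered afterwards. The downside is that censoring at last contact may itself be informative, and some community patients will contribute little or no follow-up, so the Kaplan-Meier estimates must be read together with the bounds.

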## 6. Outcome and key variables

#### 6.1. Outcome

The outcome CDI is defined as either;

- 1. a diarrhoeal sample that is *C. difficile* toxin positive using the gold standard method CCNA
- 2. a diarrhoeal sample that is *C. difficile* toxin positive using a new novel method (SIMOA)
- 3. a diarrhoeal sample that is positive for a toxigenic isolates of *C. difficile* (by either cytotoxigenic culture of toxin gene testing) AND is negative for free toxin

#### 6.2. Key variables

The following is a partial list of variables that will be collected, measured and included as potential risk factors of the analysis.

- Demographic information including age, gender, etc.

- Laboratory testing for other enteric pathogens

- Medical conditions as independent variables and as a variable based on the Charleson comorbidity index (medical conditions included are listed in appendix 1)

- Medication used including antibiotics, proton pump inhibitors, drugs affecting the gastrointestinal tract, systemic steroids or immunosuppressive drugs

- Medical procedures including acute or elective surgery and GI interventions

A detailed list of the variables and definition of the variables is attached as appendix 1.

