#### 3.1.3 Sampling Criteria for sample collection study

#### 3.1.3.1 Inclusion criteria

**ALL** unformed faecal samples (takes the shape of the container and/or stick will not remain vertical when inserted into the sample) from **ALL** patients (ALL ages) sent to the microbiology department of participating sites on their allotted testing day (irrespective of test requested).

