#### 3.1.4 Study methods

Two study days will be selected, and all diarrhoeal stool samples received on that day by the participating site in the study will be sent (regardless of test requested) to the European Coordinating Laboratory (Leeds), where samples will be tested for CDI using the recommended 'optimal' testing methodology (GDH/Toxin (Techlab, US) testing on the DS2, as per ESCMID guidelines), reference methods (cell-cytotoxicity neutralisation assay and cytotoxigenic culture) and a novel, Single-molecule Array (SiMoA) immunoassay platform for C. *difficile* toxins A and B. Samples will also be tested for other potential gastrointestinal pathogens (using the bioFire Film array molecular method), to investigate either co-infections or alternative cause of diarrhoea (where *C. difficile* negative). Results will be compared to those from the submitting hospital/laboratory, including if the sample was even tested. The SiMoA test will be carried out at bioMerieux (France), a COMBACTE-CDI partner, as the novel technology is currently not available elsewhere. A small portion of selected samples will be sent to BioMerieux for this purpose. They will only be labelled with the study number.

All data held by the study team will be pseudoanonymised to a study number. Only the original submitting laboratory will hold the code to link back to the patient. All samples will be sent for processing under the study number only.

All of the residual diagnostic stool samples will be processed in the laboratory facilities at the Healthcare Associated Infection Research Group (HCAI) at the University of Leeds. The HCAI laboratory is also the *Clostridium difficile* reference laboratory for the UK and has >20 years of experience in handling stool specimens and bacterial isolates derived from the samples. The laboratory follows all relevant regulatory processes for the UK, and all staff are fully trained in the relevant health and safety procedures. All work is risk-assessed for hazards (microbiological, chemical, and procedural) before commencement. Samples are handled in a class II Microbiological safety cabinet to protect the researcher.

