# 3.3 Case control study- objective 1.4 (risk factors)

#### 3.3.1 Study rationale

Many studies have examined risk factors associated with CDI; there are, however, three major deficiencies of existing data; (1) most studies have been performed in the epidemic setting and so may be biased by a preponderance of cases caused by one or a few strain types; (2) most studies are in hospitalised patients; (3) most were biased to patients receiving antibiotics, identified antibiotic use as the most important risk factor, and so reduced the potential to identify other modifiable risk factors. Conversely, several studies have shown that exposure to prescribed antibiotics was not present in up to 50% of CA-CDIs. CA-CDI, therefore, may be linked to other microbiota disturbing factors (other drugs, diet, etc.) currently not recognised as risk factors for CDI. Recent data have questioned whether PPIs are truly associated with CDI; earlier results may be confounded by choice of control patients.

A recent systematic review of risk factors associated with CDI recurrence and mortality noted that important variables were inconsistently reported, such as previous episodes and antibiotic use. Also, there was substantial heterogeneity and methodological limitations, including sample sizes, definitions of outcomes and follow-up periods, thus precluding a meta-analysis. We have considerable experience of determining risk factors associated with CDI. Notably, a recent University of Leeds study has determined CDI risk factors for cases determined according to a standardised diagnostic algorithm (data unpublished).

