#### 4. Study Design

This is case-control study with the cases and controls selected from the patients who had stool samples tested for CDI. The study will collect data on cases/controls (1:3 ratio) identified during the sample collection phase of COMBACTE-CDI.

For each case of confirmed CDI (or other diagnostic criteria), three controls will be randomly selected from the same participating site (i.e. if hospital case, controls will come from the same hospital, if community case, controls will come from the community). Thus initially the controls are only matched on location only, as the cohort is not large enough to enable closer matching. Subsequent further matching (e.g. by age) may be considered depending on final available sample size, but this would reduce the overall pool of controls substantially.

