#### 4.1 Inclusion-exclusion criteria

#### 4.1.1 Inclusion criteria

- 1. A case is defined as a patient who;
  - a. had a *C. difficile* toxin positive (gold standard method CCNA) stool sample
  - b. had a *C. difficile* toxin positive (new novel method –SIMOA) stool sample
  - c. had a free toxin negative stool sample but was positive for a cytotoxigenic strain (by culture or detection of toxin gene)
- 2. A Control is defined as a patient who had a sample included int eh sample collection study but tested negative by all assays

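### Other enteric pathogens and laxatives, which the protocol treats as alternative causes of diarrhoea, are candidate CDI risk factors among patients all selected for diarrhoea, so they may be ranked as protective

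*SAP*

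**What the plan says.** **Selection.** Protocol 3.1.3.1 takes every unformed stool sent to the laboratory on the sampling day, whatever test was requested. SAP 4 describes "cases and controls selected from the patients who had stool samples tested for CDI". Under SAP 4.1.1 a control is a patient in that collection who "tested negative by all assays". SAP 4.1.2 and 4.1.5 add exclusions that concern C. difficile results only. Nothing restricts controls by the cause of their diarrhoea.

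**Role in the protocol.** Protocol 3.1.4 tests for other gastrointestinal pathogens "to investigate either co-infections or alternative cause of diarrhoea". The outcome CRF list in Protocol 3.2.6 asks about an alternative cause for the patient's "diarrhoea documented (e.g. laxatives, pathogen". The risk-factor list in Protocol 3.3.6 contains neither other pathogens nor laxatives.

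**Role in the SAP.** SAP 6.2 lists "Laboratory testing for other enteric pathogens" and gut-acting drugs among variables "included as potential risk factors of the analysis". Appendix 1 marks items 3.1 (was another enteric test done within 7 days either side), 3.1.1 (its result) and 6.4/6.4.1 (gut-acting drugs in the previous 12 weeks) for both univariate and multivariate analysis. SAP 7.3 enters all the univariate variables in an unconditional logistic regression, selects forward, and uses the selection process to rank risk factors. No text says that these coefficients need a different reading.

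**The concern.** This is a comparison of CDI with other diarrhoea. Anything that produces other diarrhoea brings people into the control group and is therefore more common there than in the population that gave rise to the cases. Its odds ratio then tends to fall below 1 even if it has no bearing on CDI.

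The protocol keeps such variables apart as competing explanations for the diarrhoea. The SAP moves them into the candidate list for analysis objective 2 (risk factors). The report could then rank another enteric infection, or laxative use, as protective against CDI. A larger sample would only make that artefact more significant.

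**Working it through.** The plan gives no figure on this point, so there is none to reproduce. Every prevalence and risk multiplier below is an assumption. The counts (213 cases, of whom 39 are toxin negative, and 512 controls) are from SAP 2.1. The age, antibiotic and surgery rates are from SAP 3.

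**1. Odds ratio under no effect on CDI.** Let p be the prevalence in the source population and k the factor by which the exposure multiplies the risk of non-CDI diarrhoea.
- Case prevalence = p.
- Control prevalence = pk / (pk + 1 − p).
- Odds ratio = [p/(1 − p)] / [pk/(1 − p)] = 1/k. It is 1 only when k = 1.

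Pathogen, p = 0.05, k = 6: control prevalence 0.30/(0.30 + 0.95) = 24%; odds ratio 0.0526/0.3158 = 0.17.

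Laxative, p = 0.20, k = 2: control prevalence 0.40/(0.40 + 0.80) = 33.3%; odds ratio 0.25/0.50 = 0.50. At k = 1.5 it is 0.67 and at k = 3 it is 0.33.

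**2. If the 39 toxin-negative cases resemble controls.** The other cases number 213 − 39 = 174.
- Laxative: (174 × 0.20 + 39 × 0.333)/213 = 22.4% of cases; odds ratio 0.58.
- Pathogen: (174 × 0.05 + 39 × 0.24)/213 = 8.5% of cases; odds ratio 0.29.

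**3. Power for the laxative example (20% v 33.3%, two-sided 5%).** Power = Φ[(difference − 1.96 × pooled SE)/unpooled SE]. At 213 v 512 this is Φ[(0.1333 − 1.96 × 0.0372)/0.0344] = about 96%.

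SAP 7.3 fits the model within age groups, so pooled power is too favourable. SAP 3 has 65% of cases and 39% of controls over 65. That gives an illustrative older stratum of 0.65 × 213 = 138 cases and 0.39 × 512 = 200 controls, with power about 78%. Halving the remainder (75 and 312) gives about 37 v 156, with power about 34%.

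**4. Forward selection.** Simulations of 300 runs, 5% likelihood-ratio entry, with age (65% v 39%), antibiotics (67% v 45%), surgery (26% v 16%) and a pathogen item as candidates. Age is dropped within strata. Ranges are across repeat simulations.

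| Setting | Pathogen item 5% v 30% | Pathogen item 5% v 15% |
|---|---|---|
| 213 v 512 | always selected, first in 88–91% | selected in 97–98%, first in 1–3% |
| 138 v 200 | near-certain selection | selected in 84–88% |
| 37 v 156 | near-certain selection | selected in 45–48% |

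**5. Antibiotics.** Exact enumeration of a source population with antibiotic use 25%, pathogen 2% and laxatives 5%. The chance of causing diarrhoea is 60% for the pathogen, 20% for laxatives and 2% background. The true antibiotic odds ratio for CDI is 3.0.

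| Assumption about antibiotics | OR without the two items | OR with them |
|---|---|---|
| Cause no other diarrhoea, unrelated to the pathogen | 3.00 | 3.00 |
| Cause other diarrhoea in 0.5% of users | 2.69 | 2.45 |
| in 1% | 2.44 | 2.07 |
| in 2% | 2.05 | 1.59 |
| in 5% | 1.39 | 0.94 |
| Users carry the pathogen half as often | 3.49 | 3.00 |
| Users carry the pathogen twice as often | 2.34 | 3.00 |

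If antibiotics cause other diarrhoea, adjusting for the two items deepens the understatement. If antibiotics are only associated with the pathogen, adjusting removes the bias, which can run in either direction.

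**The case against.** **Much of a wider claim would fail.** A reader might infer that the plan understates antibiotic and PPI effects. The table in step 5 shows that this does not follow from listing these variables. It needs antibiotics to cause non-CDI diarrhoea or to be associated with the other causes, and no section says so. For PPIs there is no figure at all. Protocol 3.3.1 does say that "earlier results may be confounded by choice of control patients", but it is questioning whether the PPI association is real, not warning that it is too small. This objection stands in full.

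**Gut-acting drugs as a class.** A reader might also infer that everything under item 6.4 will look protective. The protocol names laxatives only, and the SAP does not define the class. A drug in it that does not cause diarrhoea would keep an odds ratio of 1 by this route. This stands, and it limits the point to laxatives.

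**Testing is not a result.** The SAP 6.2 line concerns testing, and item 3.1 records whether a test was done. The mechanism applies to the result, item 3.1.1. Item 3.1 mainly reflects local testing practice, which is a reason to leave it out of a CDI risk-factor model too.

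**Partly handled.** Protocol 3.1.7 already compares co-infections and alternative pathogens separately, and SAP 7.1 tabulates concomitant pathogens. Appendix item 5.9 (alternative cause) is marked univariate only, although SAP 7.3 as worded would enter it. These show the intended use of the data, but they do not take 3.1, 3.1.1 or 6.4 out of the model or the ranking.

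**Size.** The prevalences are assumed, the age strata reduce power, and at 5% v 15% the pathogen item rarely ranks first in the pooled simulation. All true. The direction under no effect on CDI does not depend on these figures.

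**Conclusion.** The point holds for the other-pathogen result and for laxatives. Each will tend to show an odds ratio below 1 to the extent that it causes non-CDI diarrhoea, with no effect on CDI required. Illustrative sizes are 0.17 (pathogen) and 0.50 (laxative, range 0.67 to 0.33 for 1.5-fold to 3-fold risk), weakening to 0.29 and 0.58 if toxin-negative cases resemble controls. Whether the artefact is selected and ranked depends on its prevalence and on the age stratum, from near-certain to about an even chance in the scenarios tried.

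This rests on three things in the documents: selection on unformed stool, controls unrestricted by cause, and the protocol's own view of these factors as alternative causes. The sizes rest on assumed prevalences. The documents do not support a general claim that antibiotic or PPI odds ratios are biased downwards. That remains conditional, and its direction depends on which condition applies. The SAP should be corrected before the risk-factor analysis is run.

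**What to change.** In SAP 6.2, SAP 7.3 and Appendix 1, remove items 3.1 and 3.1.1, and laxatives within 6.4/6.4.1, from the candidates for the CDI risk-factor model and its ranking. Report them descriptively, by case and control, as co-infection or as another explanation for the diarrhoea. This costs SAP wording and a rule for separating laxatives from the other drugs recorded under 6.4.1. No new data are needed.

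Optionally, add one sensitivity analysis that re-estimates the drug odds ratios using only controls positive for another pathogen on the bioFire panel, which Protocol 3.1.4 already plans at the central laboratory. State its downsides: fewer controls, and validity only if drug use is unrelated to those infections.
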